4.2 Exclusion Criteria

1. Non-epithelial ovarian cancers, including malignant mixed Müllerian tumors.
2. Ovarian tumors with low malignant potential (i.e. borderline tumors).
3. Relapse/progression based solely on elevation of CA-125, in absence of measurable disease (for Part A) or in the absence of measurable/non-measurable disease (for Part B), according to irRECIST criteria.
4. More than 2 prior treatment regimens for the platinum-resistant/refractory relapsed EOC, FTC, or PTC, defined as investigational, chemotherapy, hormonal, biologic, or targeted therapy.
5. Any concurrent or previous malignancy within 5 years prior to enrollment in Part A or randomization in Part B, except for adequately and radically treated basal or squamous skin cancer, or carcinoma in situ of the cervix, or other non-invasive/in-situ neoplasm. A subject with previous history of invasive malignancy (other than adequately and radically treated basal or squamous skin cancer or carcinomas in situ) is eligible provided that she has been disease free for more than 5 years.
6. Brain metastases (even if treated and/or stable), spinal cord compression, carcinomatous meningitis, or leptomeningeal disease.
7. Prior systemic anticancer therapy within 4 weeks prior to enrollment in Part A or randomization in Part B; or who has not recovered (i.e. \leq Grade 1 or baseline grade) from adverse events due to a previously administered agent
 - Notes: subjects with \leq Grade 2 neuropathy are an exception to this criterion and may qualify for the study. If subject received major surgery, they must have recovered adequately from the toxicity and/or complications from the intervention prior to starting therapy. Subjects with toxicity that has not recovered to \leq Grade 1 or baseline grade are allowed if meeting all inclusion criteria.
8. Prior treatment with a monoclonal antibody within 4 weeks prior to enrollment in Part A or randomization in Part B; or who has not recovered (i.e. \leq Grade 1 or baseline grade) from adverse events due to agents administered more than 4 weeks earlier.
 - Notes: subjects with \leq Grade 2 neuropathy are an exception to this criterion and may qualify for the study.
9. Diagnosis of immunosuppression or receiving systemic steroid therapy or any other form of immunosuppressive therapy within 7 days prior to enrollment in Part A or randomization in Part B. The use of physiologic doses of corticosteroids may be approved after consultation with the sponsor.

10. Active autoimmune disease or history of autoimmune disease or syndrome that has required systemic treatment in the past 2 years (i.e. with use of disease modifying agents, corticosteroids or immunosuppressive drugs). Replacement therapy (e.g. thyroxine, insulin, or physiologic corticosteroid replacement therapy for adrenal or pituitary insufficiency, etc.) is not considered a form of systemic treatment. Subjects with vitiligo or resolved childhood asthma/atopy will not be excluded.
11. Received live vaccines within 30 days prior to enrollment in Part A or randomization in Part B.
12. Current or prior history of myelodysplastic syndrome, leukemia or clinically significant (as per Investigator judgment) bone marrow failure.
13. Uncontrolled systemic fungal, bacterial or viral infection at time of enrollment in Part A or randomization in Part B (defined as ongoing signs/symptoms related the infection without improvement despite appropriate antibiotics, antiviral therapy and/or other treatment).
14. Known history of active TB (Bacillus Tuberculosis).
15. Known HIV infection or known history of Hepatitis B or known positivity for active Hepatitis B (HBsAg reactive) or Hepatitis C (HCV RNA [qualitative] is detected).
16. Known history of non-infectious pneumonitis that required steroids or has current pneumonitis (infectious or non-infectious).
17. Significant active cardiac disease within 6 months prior to enrollment in Part A or randomization in Part B , including but not limited to New York Heart Association class 4 cardiac heart failure, unstable angina, myocardial infarction
18. History or current evidence of any condition, therapy, or laboratory abnormality that might confound the results of the trial, interfere with the subject's participation for the full duration of the trial, or is not in the best interest of the subject to participate, in the opinion of the treating Investigator. Is or has an immediate family member (e.g. spouse, parent/legal guardian, sibling or child) who is investigational site or sponsor staff directly involved with this trial, unless prospective IRB approval (by chair or designee) is given allowing exception to this criterion for a specific subject.
19. Any contraindication to oral agents or significant nausea and vomiting, malabsorption, or significant small bowel resection that, in the opinion of the Investigator, would preclude adequate absorption.
20. Known psychiatric or substance abuse disorders that would interfere with cooperation with the requirements of the trial.
21. Prior treatment with any anti-PD-1, or PD-L1 or PD-L2 agent; or with azacitidine (any formulation) or any other hypomethylating agent; or with anti-CD137, or anti-CTLA-4 antibody (including ipilimumab) or any other antibody or drug specifically targeting T-cell co-stimulation or checkpoint pathways.
22. Known or suspected hypersensitivity to azacitidine, pembrolizumab or the excipients of any of the study drugs (including mannitol). Known or suspected hypersensitivity to monoclonal antibodies.

23. Currently participating and receiving study therapy or has participated in a study of an investigational agent and received study therapy or used an investigation device within 4 weeks prior to enrollment in Part A or randomization in Part B.
24. Pregnant or lactating women or is expecting to conceive children or breastfeed within the projected duration of the trial, starting with the screening visit through 120 days after the last dose of trial treatment.

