3.3 Part A: Determination of the Optimal Schedule for Part B

The optimal schedule to be used in Part B will be selected after analysis of the accumulated safety and efficacy data from Part A by the Steering Committee. The analyses will be conducted once 5 subjects in each cohort are considered evaluable. Subjects will be considered evaluable once they have:

- Completed at least two CC-486 cycles
- Undergone the 1st post-baseline tumor burden assessment
- Undergone the 2nd tumor biopsy and adequate paired tissue obtained

Full details of the criteria to be used to guide the Steering Committee in their selection of the optimal regimen will be described in the Steering Committee Charter. In general, however, the following decision criteria will be applied:

- Step 1: Safety and Futility evaluation:

A cohort will be rejected due to toxicity if any of the below criteria is met:

- One grade 5 AE related to study drugs
- More than one subject experiencing a grade 4 AE related to study drugs (other than hypothyroidism)

- More than 2 subjects experiencing a grade 3 AE related to study drugs (other than hypothyroidism)

A cohort will be rejected due to futility if at least one response or stable disease (irPR, irCR or irSD) is not observed in that schedule.

- Step 2: Determination of the optimal schedule: In the cohort(s) not rejected due to toxicity or due to futility, the selection by the Steering Committee of the optimal schedule will be based on the toxicity profile and the irORR of each cohort (irDCR may also be considered for the determination of the optimal schedule). For example, if one cohort has higher irORR and similar toxicity profile compared to another cohort, the first one will be selected as optimal. If two or more cohorts have the same irORR, the optimal schedule will be established based primarily on the more favorable toxicity profile. Additionally, data from the correlative analyses to be done in the biologic samples described in section 6.4.7, may be taken into consideration for determining the optimal schedule.

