4. SUBJECT SELECTION

This study can fulfill its objectives only if appropriate subjects are enrolled. The following eligibility criteria are applicable both for Part A and B of the study.

Subjects who fail to meet all inclusion criteria or fulfill at least one exclusion criteria cannot be enrolled in the study. The sponsor will not grant any eligibility waivers. If a subject that does not meet the eligibility criteria is incorrectly enrolled in Part A or randomized in Part B, the Investigator should immediately inform the Medical Monitor. The decision about the continuation or discontinuation of these subjects on the study will be based on medical judgment, treatment benefit and safety risks for the subject.

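### The closing sentence of the note to exclusion criterion 7 cancels that criterion's own recovery requirement and, on one reading, conflicts with criterion 8

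*Protocol*

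**What the plan says.** Criterion 7 in Protocol section 4.2 has two limbs. The first is a washout: "Prior systemic anticancer therapy within 4 weeks prior to enrollment in Part A" (or before randomization in Part B) excludes. The second is a recovery requirement: a subject is excluded if she has not returned to grade 1 or her baseline grade "from adverse events due to a previously administered agent".

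The note to criterion 7 makes three statements. Neuropathy up to grade 2 is an exception. Subjects who had major surgery must have recovered adequately from it. Last, subjects whose toxicity remains above "Grade 1 or baseline grade are allowed if meeting all inclusion criteria".

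Criterion 8 concerns earlier monoclonal antibodies. It repeats the recovery bar, there for subjects not recovered "from adverse events due to agents administered more than 4 weeks earlier". Its note has the neuropathy exception but no sentence admitting unrecovered subjects.

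Section 4 governs all of this: "Subjects who fail to meet all inclusion criteria or fulfill at least one exclusion criteria cannot be enrolled in the study". It adds: "The sponsor will not grant any eligibility waivers".

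The wording of criteria 7 and 8 is the same in the protocol synopsis and in the synopsis reproduced as SAP Appendix 6.1.

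**The concern.** A criterion and its own note give opposite answers for the same subject. A site that reads the criterion excludes her; a site that reads the note enrols her. Both act on approved text. This affects both parts of the trial, because section 4 applies the eligibility criteria to Part A and Part B alike.

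There is also a possible link to schedule selection. Protocol section 3.3 rejects a Part A cohort on small counts, for example "More than 2 subjects experiencing a grade 3 AE related to study drugs" (hypothyroidism apart), or more than one subject with a related grade 4 event. With about five evaluable subjects per cohort, it matters who may enter with toxicity already present. How far that link holds is examined below.

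**Working it through.** The plan states no figure on this point, so the check is mainly a comparison of texts.

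**Step 1. Does the note's condition restrict anyone?** The note admits unrecovered subjects who meet all inclusion criteria. Section 4 requires that of every enrolled subject. The subjects admitted by the note are therefore all otherwise eligible subjects who fail the recovery limb, and that limb excludes nobody.

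**Step 2. What else in criterion 7 is affected?**
- Washout limb: untouched, because the sentence concerns toxicity and not the timing of treatment.
- Surgery requirement: untouched, because it uses a separate standard of adequate recovery.
- Neuropathy exception: redundant. If unrecovered toxicity of any kind is admitted, a specific exception up to grade 2 adds nobody. This suggests that the last sentence was not drafted together with the rest.

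**Step 3. How does criterion 8 fit?** There are two readings of the word agents in its recovery limb.
- Any earlier agent. The washout in criterion 7 already puts earlier systemic anticancer therapy outside the 4-week window. Criterion 8 would then exclude nearly all the subjects whom the note to criterion 7 admits, which is a direct conflict.
- Monoclonal antibodies only. Criterion 8 then bars unrecovered toxicity from antibodies, while the same grade of toxicity from other drugs is admitted under criterion 7. This is a difference that the documents do not explain.

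**Step 4. Can such toxicity reach the Part A counts?**
- Section 3.3 counts only events judged related to study drug.
- Section 7.1.2 does not require a baseline condition that stays the same to be reported as an adverse event, but any worsening is reported.
- Section 7.2.2 makes relatedness a yes/no judgment by the investigator for each event.
- SAP section 3.5.2 tabulates events by relationship and maximum grade and states no adjustment for baseline grade.

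Taken together, an admitted subject counts only if her toxicity worsens to grade 3-4 on study and is judged related.

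**Step 5. Scale, for illustration only.** Assume n = 5 subjects and independent events with per-subject probability p of a related event. The values of p are assumptions. Without a carried-over case, P(reject) is P(X ≥ 3) of 5 under the grade 3 rule and P(X ≥ 2) of 5 under the grade 4 rule. If one subject is already counted through worsened baseline toxicity, these become P(X ≥ 2) of 4 and P(X ≥ 1) of 4.

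| Rule | p | No carried-over case | One already counted |
|---|---|---|---|
| Grade 3 | 0.1 | 0.009 | 0.052 |
| Grade 3 | 0.2 | 0.058 | 0.181 |
| Grade 3 | 0.3 | 0.163 | 0.348 |
| Grade 3 | 0.4 | 0.317 | 0.525 |
| Grade 4 | 0.05 | 0.023 | 0.185 |
| Grade 4 | 0.1 | 0.081 | 0.344 |
| Grade 4 | 0.2 | 0.263 | 0.590 |

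For example, at p = 0.1 under the grade 4 rule, 1 − 0.9⁴ = 0.344. The last column is conditional on the event having occurred. It shows that one counted subject matters in a small cohort. It does not show how likely the event is.

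**The case against.** The strongest reply is that other provisions limit who could enter through the note. Inclusion 11 sets laboratory limits within 7 days of enrollment or randomization, and section 6.3.1 requires repeat values before treatment to meet them. ECOG status must be 0 or 1. Exclusions 13, 16, 18 and 19 cover uncontrolled infection, pneumonitis, conditions that might confound the results, and nausea or vomiting that would preclude adequate absorption. The sponsor also reviews screening data centrally and confirms eligibility for each subject (sections 6.1.2.1 and 6.1.2.2), so one reading could be applied uniformly, and Part A has only four sites. The note may simply have been meant to defer to the laboratory limits in inclusion 11.

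Much of this stands as mitigation, but it does not remove the contradiction. No inclusion criterion caps the grade of clinical toxicity such as diarrhea or fatigue, which section 1.3.1 lists among the commonest reactions to oral azacitidine. Exclusion 18 rests on the investigator's opinion. Central review works from the same conflicting text. The rule against waivers does not settle the matter either, because an exception written into a criterion is not a waiver. The difference between criteria 7 and 8 may be deliberate if criterion 8 concerns antibodies only, but its text does not say so.

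A reader might go further and infer that criterion 7 is void as a whole, or that carried-over toxicity enters the Part A counts as such. Steps 2 and 4 of the working show that the documents support neither.

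**Conclusion.** The text is wrong as written. The note cancels the recovery limb of criterion 7, makes the neuropathy exception redundant and, if agents in criterion 8 is read broadly, conflicts with that criterion. This rests on the wording alone and needs no assumption about event rates.

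The consequence for Part A is narrow and cannot be sized from the documents. They do not say how many unrecovered subjects would be admitted, how many would worsen to grade 3-4, or how many of those events would be judged related. A reader might infer from the thresholds that one admitted subject supplies a third (1 of 3, grade 3) to a half (1 of 2, grade 4) of the events needed to reject a cohort. That is only the share that any subject with a qualifying event contributes, and it does not measure this defect. Five is also the minimum number of evaluable subjects. Non-evaluable subjects are replaced, and the SAP's Safety Population takes in everyone treated, so the number at risk may be larger.

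No endpoint definition, sample size, power or alpha figure depends on the point. It matters because it is a rule applied to every subject, bears on safety and consistent enrollment, and is easily corrected.

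**What to change.** Reconcile criterion 7, its note and criterion 8 in Protocol section 4.2 so that they state one rule on recovery from earlier toxicity. Say in criterion 8 whether its recovery limb covers antibodies only or any earlier agent. Carry the same text to the protocol synopsis and to SAP Appendix 6.1. Which rule applies is for the sponsor to decide.

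If the reconciled rule does admit subjects with unrecovered toxicity, it would help to add a line to section 3.3 and SAP section 3.5.2 on how events that worsen from a baseline grade are counted.

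The eligibility correction costs about one sentence changed or removed, a clarification in criterion 8, and matching edits in the two synopses, all in one amendment. It needs no new data collection and no change to the sample size.

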5. TREATMENT

In the TRIO026 study, CC-486 and pembrolizumab are both considered Investigational Medicinal Products (IMP) given their intended use and the objectives of the study. Collectively they are referred as “study treatments”.

In both parts (A and B), subjects will remain on their assigned study treatment until progressive disease based on irRECIST, unacceptable toxicity, consent withdrawal, Investigator’s decision that it is in the subject’s best interest to discontinue or other treatment withdrawal criteria is met (section 5.5).

5.1 CC-486

All subjects in Part A and subjects randomized to Arm A of Part B will receive oral CC-486 at the dosing described in sections 5.3.3 and 5.3.4.

At each visit during the treatment phase, subjects should be given container(s) with enough 100 mg tablets for one full CC-486 treatment cycle (defined as 21 or 14 days on-treatment followed by 7 or 14 days off-treatment (depending on the cohort)) of the corresponding schedule/arm (refer to section 5.3).

In Part A, the following number of 100 mg tablets would be needed for a subject to complete one CC-486 cycle of treatment, assuming no dose delays or interruptions or dose reductions from the starting dose level:

- Schedule 1: 21 tablets of 100 mg
- Schedule 2: 42 tablets of 100 mg
- Schedule 3: 42 tablets of 100 mg
- Schedule 4: 63 tablets of 100 mg

The number of tablets may need to be adjusted in case of dose modifications.

For the purpose of this trial, the Single Reference Document to be used for CC-486 is the azacitidine IB.

5.2 Pembrolizumab

Pembrolizumab will be administered in all cohorts in Part A and in both arms in Part B at a fixed dose of 200 mg as a 30 minute IV infusion. Sites should make every effort to target infusion timing to be as close to 30 minutes as possible.

In all cohorts in Part A and in Arm A of Part B, the first pembrolizumab infusion will be administered 7 days (\pm 3 days) after commencing treatment with CC-486 and thereafter all subsequent infusions will be administered every 21 days (\pm 3 days).

For the purpose of this trial, the Single Reference Document to be used is the pembrolizumab IB.

5.3 Dosage and Administration

5.3.1 Pre-medications

5.3.1.1 Antiemetics for Prevention and Treatment of Emesis

Drugs with the highest therapeutic index for the management of treatment induced nausea and vomiting are the type three 5-hydroxytryptamine (5-HT₃) receptor antagonists and the neurokinin-1 receptor (NK1R) antagonists. Additionally, recent data has demonstrated substantial antiemetic activity for the antipsychotic medication olanzapine when used in combination with other antiemetics.

The following antiemetic medication is recommended for CC-486:

- Prophylactic 5-HT₃ antagonist should be considered on days when CC-486 is administered.
- Prochlorperazine and/or 5-HT₃ inhibitor could also be considered for delayed nausea as needed.
- If subjects experience nausea sub-optimally controlled with prochlorperazine on the days of CC-486 administration, prophylactic 5-HT₃ inhibitors may be used.
- If nausea and vomiting persists despite the above measures, more aggressive use of 5-HT₃ antagonists or other anti-emetics could be used at the discretion of the treating physician. In cases of nausea and/or vomiting insufficiently controlled by prophylactic treatment with a 5-HT₃ receptor antagonist, antiemetic therapy with a combination of an NK1R antagonist and a 5-HT₃ receptor antagonist and consideration of olanzapine is recommended.

5.3.1.2 Antidiarrheals

Although premedication for diarrhea prophylaxis is not required, proactive management of first signs of diarrhea is strongly recommended according to section 5.7.3.2. Prophylaxis can be considered as per investigator's best clinical judgement and local practice.

5.3.1.3 Pembrolizumab Premedication

No specific pre-medication is required upfront for pembrolizumab. However pre-medications may be given as per the institutional standard of care.

5.3.2 Preparation

5.3.2.1 CC-486

Not applicable.

5.3.2.2 Pembrolizumab

Preparation should be done in accordance with the Single Reference Document for pembrolizumab and with site's standard procedures for preparing pembrolizumab.

5.3.3 Study Treatment Administration in Part A

Eligible subjects will receive pembrolizumab 200 mg IV every 21 days (\pm 3 days) combined with one of the below four schedules of CC-486:

- Schedule 1: CC-486 100 mg q.d. 21 days on, followed by 7 days off-treatment.
- Schedule 2: CC-486 100 mg BID 21 days on, followed by 7 days off-treatment.

- Schedule 3: CC-486 300 mg q.d. 14 days on, followed by 14 days off-treatment.
- Schedule 4: CC-486 300 mg q.d. 21 days on, followed by 7 days off-treatment.

For each subject, the corresponding study treatment schedule will be assigned according to the process described in section 6.1.2.1.

On the first CC-486 cycle, after 7 days (± 3 days) of CC-486 monotherapy, the first pembrolizumab administration will be done and thereafter subsequent pembrolizumab infusions will be given every 21 days (± 3 days). CC-486 will continue according to the applicable schedule.

Treatment duration with CC-486 is fixed to 21 consecutive days for schedules 1, 2 & 4, and to 14 consecutive days for schedule 3, regardless of treatment interruptions for any reason. The treatment period with CC-486 must always be followed by the 'off treatment period' defined for each of the treatment schedules.

Subjects will remain on their assigned treatment until progressive disease based on irRECIST, unacceptable toxicity, consent withdrawal, the Investigator concludes that it is in the subject's best interest to discontinue, or other treatment withdrawal criteria is met (section 5.5).

If a subject is enrolled in Part A but does not receive any study treatment, the reason must be documented in the electronic case report form (eCRF). Baseline data will be collected and subject will undergo the End of Treatment visit (even if no treatment administered) and will be taken off the study.

5.3.3.1 CC-486 intake instructions

CC-486 should be taken at the same time each day (± 2 hours). When taken twice a day, CC-486 should be taken approximately every 12 hours, in the morning and at night. CC-486 may be taken on an empty stomach or with food (a light breakfast or meal of up to approximately 600 calories). Subjects will ingest CC-486 whole tablets with approximately 240 mL (8 ounces) of room temperature water. No tablet should be ingested if it is broken, cracked, or otherwise not intact.

If the subject misses a dose of CC-486, she should take the dose as soon as possible, but not more than 6 hours after the missed scheduled dose. If greater than 6 hours, the missed dose should be skipped and the subject should take the next dose when scheduled. No "make-up dose" or increased dosing should occur.

If vomiting occurs following CC-486 administration, subjects should not take additional drug on that same day. It is recommended that the subject receives an antiemetic (e.g. ondansetron) 30 minutes prior to all subsequent CC-486 doses.

5.3.3.2 CC-486 Intake: Specificities on Day 1 of the First CC-486 cycle (all schedules)

In all schedules, the first CC-486 intake in the study (i.e. on the first CC-486 cycle) should be taken by the subject during the clinic visit and after the whole blood sample for DNA methylation was drawn.

Subject must arrive to the clinic in the fasting state (i.e. no food or drink [except water] for approximately 8 - 10 hours) for the required pre-dose assessments (DNA methylation blood sample and safety evaluations as per section 6.4 if applicable). Once these assessments are completed, subjects will ingest CC-486 with 240 mL of room temperature water in the clinic.

5.3.3.3 Treatment Regimen for Schedule 1

The treatment to be used in the trial is outlined below in Figure 4.

[figure not shown]

Figure 4: Treatment regimen for Schedule 1

Notes:

- Within 3 days of enrollment, study treatment will begin with CC-486 monotherapy. After 7 days (\pm 3 days) of CC-486 treatment, the first pembrolizumab administration will be done.
- Pembrolizumab will be administered at a dose of 200 mg as a 30-minutes IV infusion every 21 days (\pm 3 days). Sites should make every effort to target infusion timing to be as close to 30 minutes as possible.
- CC-486 is administered 100 mg orally once daily, 21 days on treatment followed by 7 days off. CC-486 may be taken on an empty stomach or with food (a light breakfast or meal of up to approximately 600 calories). Whole tablets of CC-486 must be taken with approximately 240 mL (8 ounces) of room temperature water.
- On days when both CC-486 and pembrolizumab are administered, pembrolizumab will be infused after CC-486 intake.
- Refer to section 5.7 for treatment schedule adjustments.

5.3.3.4 Treatment Regimen for Schedule 2

The treatment to be used in the trial is outlined below in Figure 5.

[figure not shown]

Figure 5: Treatment regimen for Schedule 2

Notes:

- Within 3 days after enrollment, study treatment will begin with CC-486 monotherapy. After 7 days (± 3 days) of CC-486 treatment, the first pembrolizumab administration will be done.
- Pembrolizumab will be administered at a dose of 200 mg as a 30-minutes IV infusion every 21 days (± 3 days). Sites should make every effort to target infusion timing to be as close to 30 minutes as possible.
- CC-486 is administered 100 mg orally twice a day (approximately every 12 hours, in the morning and at night), 21 days on treatment followed by 7 days off. CC-486 may be taken on an empty stomach or with food (a light breakfast or meal of up to approximately 600 calories). Whole tablets of CC-486 must be taken with approximately 240 mL (8 ounces) of room temperature water.
- On days when both CC-486 and pembrolizumab are administered, pembrolizumab will be infused after the first CC-486 intake on that day.
- Refer to section 5.7 for treatment schedule adjustments.

5.3.3.5 Treatment Regimen for Schedule 3

The treatment to be used in the trial is outlined below in Figure 6: Treatment regimen for Schedule 3

[figure not shown]

Figure 6: Treatment regimen for Schedule 3

Notes:

- Within 3 days of enrollment, study treatment will begin with CC-486 monotherapy. After 7 days (± 3 days) of CC-486 treatment, the first pembrolizumab administration will be done.
- Pembrolizumab will be administered at a dose of 200 mg as a 30-minutes IV infusion every 21 days (± 3 days). Sites should make every effort to target infusion timing to be as close to 30 minutes as possible.
- CC-486 is administered 300 mg orally once daily, 14 days on treatment followed by 14 days off. CC-486 may be taken on an empty stomach or with food (a light breakfast or meal of up to approximately 600 calories). Whole tablets of CC-486 must be taken with approximately 240 mL (8 ounces) of room temperature water.
- On days when both CC-486 and pembrolizumab are administered, pembrolizumab will be infused after CC-486 intake.
- Refer to section 5.7 for treatment schedule adjustments.

5.3.3.6 Treatment Regimen for Schedule 4

The treatment to be used in the trial is outlined below in Figure 7: Treatment regimen for Schedule 4

[figure not shown]

Figure 7: Treatment regimen for Schedule 4

Notes:

- Within 3 days of enrollment, study treatment will begin with CC-486 monotherapy. After 7 days (± 3 days) of CC-486 treatment, the first pembrolizumab administration will be done.
- Pembrolizumab will be administered at a dose of 200 mg as a 30-minute IV infusion every 21 days (± 3 days). Sites should make every effort to target infusion timing to be as close to 30 minutes as possible.
- CC-486 is administered 300 mg orally once daily, 21 days on treatment followed by 7 days off. CC-486 may be taken on an empty stomach or with food (a light breakfast or meal of up to approximately 600 calories). Whole tablets of CC-486 must be taken with approximately 240 mL (8 ounces) of room temperature water.
- On days when both CC-486 and pembrolizumab are administered, pembrolizumab will be infused after CC-486 intake.
- Refer to section 5.7 for treatment schedule adjustments.

